## consent

- Describe the steps that will be taken by the research team to minimize the possibility of coercion or undue influence during the consent process

For Aim 1, participants will include approximately 250 adults who are current smokers from the Greater St. Louis Area. The research team will recruit subjects from the existing COGA study (IRB ID 201105402) and GISC study (IRB ID 201305128), including only those who are current smokers, and will also Epic/MyChart and work with Volunteer for Health (VFH) to identify and enroll individuals who are current smokers and at least 18 years of age. Participants can search for and volunteer to be enrolled in this study or may be identified as potentially eligible for this study. Through word-of-mouth, participants may also provide us with contact information for others who may be interested in participating. Once identified, the principal investigator will send the postal mail recruitment letter or email recruitment letter to potential participants who can then contact the research team to find out more about the study and set up an in-person or electronic consent (e-Consent) and screening visit or phone call, as desired. Informed consent will be obtained from all subjects by a trained research assistant. E-Consent will be conducted in REDCap, and we will email to the participant a link to the e-Consent to complete. Participants will be able to download or print a copy of the consent from REDCap. Participants will have the option to receive a signed copy of their consent emailed to them by the research team via REDCap. During the in-person consent visit or e-Consent, participants will be provided with a copy of the consent form for review and given the opportunity to ask questions prior to agreeing to participate. Participants will be assured that they can choose not to participate or can discontinue participation at any time without losing any benefits for which they would otherwise qualify. Participants for this study will also be invited to consent to be enrolled in the ICTS Genomic Database Protocol (IRB# 201902019). This protocol allows their genetic data, research data and electronic health care data to be placed in the ICTS Genomic Database for future research. Details for the ICTS Genomic Database Protocol are provided in the ICTS Genomic Database IRB.

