For Aim 1, via in-person or remote (phone or Zoom) interviews, we will ask baseline questions about smoking behaviors and genetic knowledge and then offer genetic testing to the participant. As an objective measure of acceptability, we will track the proportion of eligible participants who decline the genetic testing; this will inform how many individuals must be targeted to achieve desired samples in future research. This interview will take approximately 20 minutes. During the in-person visit, participants will contribute DNA via saliva sample; during remote visits, participants will contribute DNA via saliva sample using a 23andMe kit that was mailed to them. We will give each participant a tube to collect each saliva sample. Participants will spit into the tube until there is enough saliva in the tube. This typically takes 1 to 5 minutes. The research team (for in-person visits) or the participant (for remote visits) will send the saliva samples to 23andMe for genetic testing and analysis in a CLIA certified laboratory. Saliva samples sent to 23andMe will be registered via an on-line account created by the participant on the 23andMe website using their personal email address. Participants must provide first and last name, sex and date of birth to register their saliva sample. During the in-person or remote visit, participants will register their sample with 23andMe, including ancestry and health information, and will authorize the research team to receive their results but will not automatically agree to other research through 23andMe. A member of the research team will assist participants in creating an online account through the 23andMe website. Participants can choose whether or not they want 23andMe to store their saliva sample. A member of the research team will show participants this option on the 23andMe website while helping them to register their sample. We will ask participants to log into their 23andMe account and give permission for the research team to download their genetic data and use it for research purposes. We will use these data to create a personalized genetic profile (RiskProfile) specific to participants' smoking-related genetic risk and likely responsiveness to medication. The data used for genomic profiles that we will create are part of the standard data generated by 23andMe. We will then randomize participants to one of two groups--Intervention (receive RiskProfile) or Control (receive brief cessation counseling and then receive RiskProfile at end of study)--and ask participants to return for a separate in-person or remote visit to receive their personalized genetic profile or brief cessation counseling and respond to the interview questions during that in-person or remote visit. The personalized genetic profile will be referred to as a genetics-informed "RiskProfile" and was refined through the developmental/design-oriented study with multiple stakeholder groups. Depending on the specific genetic profile of the participant, the RiskProfile will slightly differ; for example, for some, it will say "at very high risk", for some, it will say "at high risk", and for some, it will say "at risk". This will enable us to receive important feedback about the return of results procedure within the context of recently receiving personalized genetic results profile. These participants will then be asked to participate in a 30-day follow-up and then a 6-month follow-up, both comprising a 20-minute interview by phone or Zoom to examine changes in attitude and behavior as a result of receiving their personalized genetic results profile. Control group participants will receive their RiskProfile during the 6-month follow-up assessment. For the remote study, each participant's unique RiskProfile will be stored in the participant's unique folder on WUSTL Box platform and viewable to that participant and the research team only. Participants will also be asked to do a brief 10-15 minute phone follow-up approximately 18 months after their intervention to see if changes in attitude and behavior as a result of receiving their personalized genetic results profile have persisted.

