Attachment Name	Category	Version	Date Attached
Aim 2_V1 Assessment_07142023.docx	Subject Data Collection Instruments	1	07/14/23
Aim 2_Clinician V2 Assessment.docx	Subject Data Collection Instruments	1	07/14/23
Eligibility Screener for Focus Groups.docx	Subject Data Collection Instruments	1	10/07/22
V5 Assessment_7-10-23.docx	Subject Data Collection Instruments	4	07/11/23
V1 Assessments_08052021.docx	Subject Data Collection Instruments	15	08/05/21
Aim 2_V2 Assessment_071423.docx	Subject Data Collection Instruments	1	07/14/23
Open Ended Interview Questions_082620.docx	Subject Data Collection Instruments	7	08/28/20
Eligibility Script for GENIMP2_011421(1).docx	Subject Data Collection Instruments	4	01/14/21
V4 Assessments_7-10-2023.docx	Subject Data Collection Instruments	12	07/11/23
Locator Form.docx	Subject Data Collection Instruments	1	06/25/19
Script for Report Card Design Feedback_071919.docx	Subject Data Collection Instruments	5	07/22/19
GENIMP Aim 2_Focus Group Guide Final.docx	Subject Data Collection Instruments	1	10/07/22
V2 Assessments_7-10-23.docx	Subject Data Collection Instruments	17	07/11/23
V3 Assessments_7-10-23.docx	Subject Data Collection Instruments	17	07/11/23

**1.16** Does this project involve creating any audio, video, or photographs?

Yes

- 1.17** Does the study include any form of deception (e.g., providing participants with false information, misleading information, or withholding information about certain study procedures)?

Examples:

- Procedure includes a cover story that provides a plausible but inaccurate account of the purposes of the research.
- Participants will be provided with false information regarding the particular behaviors of interest in the research.
- Procedures include a confederate pretending to be another participant in the study.
- Participants will be told that the research includes completion of a particular task, when in fact, that task will not be administered.
- Study is designed to introduce a new procedure (or task) that participants are not initially told about.

No

- 1.18** Indicate any payments or reimbursements to participants (check all that apply)

- Cash
- Check
- Gift or Debit Card
- Forte Debit Card

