- 1.19** Does this study have a plan to have an individual or committee review combined data from all participants on a periodic basis (such as summary or aggregate safety and/or efficacy data)?

No

- 1.20** What have you done to minimize any risks?

- No foreseeable risks

- 1.21** What are the potential benefits related to this project for:

- the participant (if any)
- benefits to society (if any)

Participants (adults who smoke) will have the direct benefit of receiving their individual genomic results profiles which could potentially improve their health behaviors (e.g., reduce tobacco use) and effectiveness of their treatment plans. Participants will receive genetic testing by 23andMe at no cost to them. From 23andMe they will receive genetic ancestry results and health results including carrier status reports, trait reports, and wellness reports.

The potential benefits to society are significant if the proposed research increases understanding of the best approaches to integrating genomic findings for substance use disorders into diverse settings. It is possible that the results of this study could be used to improve smoking and substance use disorder prevention and treatment strategies.

- 1.22** Provide a summary of the analysis methods you will use, including, if applicable, the data points or outcomes you will analyze.

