For Aim 1, we will assess the acceptability of using genomic results (i.e., % agreeing to genetic testing, sharing results with others, recalling personal genomic results) and test whether smoking behaviors (frequency, heaviness) change more following delivery of the RiskProfile intervention than following brief cessation counseling. We expect higher rates of smoking cessation and reduction the Intervention group, particularly for those who accepted and recall their genomic results and whose health-related cognitions were altered (e.g., increased perceptions of disease risk, cessation benefits, value of cessation medications, self-efficacy). We will also examine whether the acceptability and recall of their genomic data for smoking cessation differ by age, sex, race, education level, or initial smoking behaviors. Given prior research on disparities in use of genomic results, we anticipate that acceptability and recall of results, or other mechanisms of behavior change, may be lower in African Americans, men, and heavier smokers. We will conduct multiple linear regression analyses to determine the extent to which race, initial smoking heaviness, or level of genetic risk predict acceptability and recall of genomic results, and whether receiving the RiskProfile predicts smoking cessation or reduction.

For Aim 2, we will identify key themes that will guide the adaption and improvement of the RiskProfile to deliver the tool in real-world settings. Adapting the RiskProfile will include data points consisting of refining the content, format, and delivery mode.

- 1.23** Provide the rationale or power analysis to support the number of participants proposed to complete this study.

Prior samples of a similar size and nature have allowed for adequate generalizability and power to detect relationships between variables of interest, including the ability to detect moderating relationships through interaction analyses. The current study is expected to mirror this prior experience, yielding adequate validity and range of responses. However, this study stands on its own as a pilot project, and any challenges related to power analysis do not negate the usefulness of this small-scale project to demonstrate proof of concept, establish the feasibility of returning genomic results to patients and physicians in a clinical setting, and provide the necessary rationale to test these implementation approaches with larger samples in future research.

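### The arms have different reasons to attend the 6-month visit, and the planned linear regression has no stated protection if loss differs by arm and is related to smoking

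*Combined protocol and SAP*

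**What the plan says.** Section 1.13 randomises Aim 1 participants to receive the RiskProfile at the next visit, or to "Control (receive brief cessation counseling and then receive RiskProfile at end of study". On follow-up it says "These participants will then be asked to participate in a 30-day follow-up and then a 6-month follow-up", each a 20-minute interview by phone or Zoom. On timing for controls it says "Control group participants will receive their RiskProfile during the 6-month follow-up assessment". No primary time point is named.

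Section 1.21 treats the RiskProfile as something of value: "Participants (adults who smoke) will have the direct benefit of receiving their individual genomic results profiles".

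Section 1.22 compares change in smoking frequency and heaviness between the arms and expects more cessation and reduction with the RiskProfile. The method is given as "We will conduct multiple linear regression analyses". It states no analysis set, no handling of missing outcomes, no sensitivity analysis and no report of retention by arm. Section 1.1 of the Protocol part says that there is no separate written protocol, so 1.22 is the analysis plan. Section 1.23 gives no dropout assumption.

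**The concern.** At 6 months a control participant is still waiting for the RiskProfile and an intervention participant is not. That is a reason to attend in one arm only, and it falls on the last assessment before controls receive the intervention.

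Unequal incentives do no harm by themselves. They matter if they lead to unequal loss and the people lost differ in smoking from the people kept. A regression fitted to those with an outcome then compares two differently selected groups, and randomisation no longer protects the comparison. Section 1.3 makes the preliminary effect of the RiskProfile against counselling one aim of the pilot, and section 1.23 looks to the pilot to justify larger studies. A distorted estimate could therefore carry forward.

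**Working it through.** The plan gives no retention, power or effect figure to reproduce, so this is an illustration on labelled assumptions.

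**Inputs**
- True effect: none (assumed), with the same true rate *p* in both arms.
- Loss at 6 months: 10% in controls (assumed); 25% in the intervention arm (assumed), range 20% to 30%.
- *p* for cessation: 10% (assumed), with 5% as a low case. Section 1.5 (C1) says about 5% of smokers manage to quit.
- Sample: about 250 in Aim 1 (section 1.12). For false-positive rates I assume that all are randomised 1:1, giving 125 per arm, and a two-sided 5% test.

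**Formula.** If dropouts quit at *k* times the arm's rate, the rate among those observed is *p*(1 − *k* × loss)/(1 − loss). With *k* = 0, every dropout is still smoking.

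**Results for *p* = 10%, loss 10% v 25%**

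| Who drops out | Control observed | Intervention observed | Gap (points) |
|---|---|---|---|
| All continuing smokers (*k* = 0) | 0.10/0.90 = 11.1% | 0.10/0.75 = 13.3% | +2.2 |
| Quit at half the rate (*k* = 0.5) | 0.10 × 0.95/0.90 = 10.6% | 0.10 × 0.875/0.75 = 11.7% | +1.1 |
| Unrelated to outcome (*k* = 1) | 10.0% | 10.0% | 0 |
| Quit at twice the rate (*k* = 2) | 0.10 × 0.80/0.90 = 8.9% | 0.10 × 0.50/0.75 = 6.7% | −2.2 |

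**Range for *k* = 0, *p* = 10%.** Intervention loss of 20% gives 0.10/0.80 = 12.5%, a gap of +1.4 points. Loss of 30% gives 0.10/0.70 = 14.3%, a gap of +3.2. With *p* = 5% and 25% loss the rates are 5.6% v 6.7%, a gap of +1.1.

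**False positives for *k* = 0, 25% loss** (normal-approximation two-proportion test): about 6.5% at *p* = 5% and 7.9% at *p* = 10%, against a nominal 5%. At *p* = 10% and 30% loss the figure is 10.7%.

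**Amount smoked.** Bias in SD units = (difference in loss) × (how much worse dropouts are than those observed, in SD). If dropouts are 0.5 SD worse in both arms (assumed), 10% v 25% loss gives 0.15 × 0.5 = 0.075 SD in favour of the intervention.

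**Counting missing as smoking.** In the *k* = 0 case this recovers 10% v 10%. If loss is unrelated to smoking it gives 0.10 × 0.90 = 9.0% v 0.10 × 0.75 = 7.5%, a false harm of 1.5 points.

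**The case against.** The documents establish an unequal incentive, not unequal dropout, and this objection stands. There is no retention figure by arm. Section 1.18 lists types of payment without amounts or any difference by arm, the interview is short and remote, and the 23andMe reports in section 1.21 are not tied to the 6-month visit. Payments equal in both arms would leave the difference in incentive in place, but they could keep loss low in both. Controls who agreed to genetic testing and were then given counselling might even leave sooner.

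A reader might infer that controls must attend or lose the RiskProfile. The documents do not say so. Section 1.12 assures participants that they "can discontinue participation at any time without losing any benefits for which they would otherwise qualify", although that is general consent wording. The Return of Results Plan listed in section 1.26.c may settle the matter, but it is not part of the text available here.

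A reader might also infer that the plan chose to analyse available data only. It did not: section 1.22 is silent, and omission of people without an outcome is the default behaviour of the method it names.

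Finally, a reader might infer that the design produces a false benefit. The table shows that the sign depends on who leaves, and that random loss gives no bias at all.

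What the objection does not remove is that an arm-specific incentive at the last assessment before crossover meets an analysis with no stated protection in either direction.

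**Conclusion.** The concern holds as a conditional one. The RiskProfile reaches controls at the 6-month assessment, so the arms have different reasons to attend, and section 1.22 plans a regression that by default drops those without an outcome. If loss then differs by arm and is related to smoking, the comparison is biased.

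On assumed losses of 10% and 25% with a true 10% quit rate and no effect, the false gap runs from +2.2 points (all dropouts smoking, the worst case for a false benefit at those losses) through zero (loss unrelated to outcome) to −2.2 points (dropouts quitting at twice the rate). The losses and the link to smoking are assumptions. At cessation rates of 5% to 10% the rise in false positives is modest for a pilot. The point is worth acting on because the remedy is cheap and uses visits already planned.

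**What to change.** In section 1.22:
- State that all randomised participants are analysed by assigned arm.
- For amount smoked, replace the linear regression with a mixed model on the baseline, 30-day and 6-month data. People seen at 30 days but lost at 6 months then stay in, which removes bias from loss that earlier smoking predicts. This presumes that the smoking measure is recorded at all three contacts.
- For cessation, use multiple imputation that includes the 30-day data. Make missing-equals-smoking a sensitivity analysis, alongside departures from the imputation assumption in both directions. It should not be the only rule, because it can turn the bias against the intervention.
- Report retention by arm and visit.

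It would also help to state in section 1.13 whether a control who misses the 6-month contact still receives the RiskProfile.

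The cost is a few sentences and slightly more analysis work. The mixed model and the imputation still rely on data being missing at random given what was observed, so they do not fully remove loss driven by unobserved smoking. The sensitivity analyses are there for that reason.

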Aim 1: Examine the acceptability and effect of personalized genomic results on smoking behaviors, also referred to as the RiskProfile, in different subgroups of adult smokers. As an important pre-implementation step, we will examine the extent to which smokers in the community (1) agree to genetic testing, (2) recall details of their personalized genomic results, and (3) change their smoking behaviors following review of their results. We will give particular attention to potential differences in outcomes between subgroups, including African Americans and European Americans. We will also examine potential mechanisms of behavior change, including health-related cognitions and engagement, that may explain the observed outcomes (acceptability and effect of the RiskProfile).

Aim 2: Adapt the RiskProfile and evaluate feasibility and acceptability for use in real-world community settings. In this mixed methods approach, we will aim to conduct an iterative process of data collection and adaption to determine the feasibility of delivering the RiskProfile in a real-world setting. There are two data sources that will inform the adaptation of the RiskProfile: 1) adapting for internal validity, using evidence from Aim 1 on potential mechanisms that may identify elements that need to enhance potency of the intervention, and 2) adapting for

external validity, using focus group feedback from a sample representing patient and provider viewpoints on necessary modifications to the RiskProfile for use in a community health agency setting.

Feasibility of delivering the adapted RiskProfile will be determined by conducting a small-scale feasibility trial among current smokers using structured interviews and quantitative metrics to examine the extent to which the RiskProfile is translatable to real-world community settings. We hypothesize that successful completion of this aim will generate feasibility and acceptability data that will support standardized use of the RiskProfile by community-based providers in real-world settings.

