## 1.5 Background and significance and/or Preliminary studies related to this project:

### C. SIGNIFICANCE

C1. Substance use disorders, including tobacco use disorders, are a major public health problem. Tobacco use remains the largest cause of preventable death in the United States, contributing to chronic obstructive pulmonary disease, myocardial infarction, at least 14 types of cancer, and numerous other medical illnesses. Harmful effects of smoking cost the United States more than \$200 billion each year in health and productivity-related costs and will eventually kill half of those who regularly use tobacco. There are several evidence-based pharmacotherapies for smoking cessation—including varenicline, nicotine-replacement therapies, and bupropion—and 70% of smokers currently want to quit. Nevertheless, sustained patient engagement and adherence to treatment are low, and only about 5% of smokers are able to successfully quit smoking, suggesting the need for improved personalized smoking cessation treatment protocols.

C2. Genomic data predict heaviness of smoking, risk of smoking-related diseases, and effect of smoking cessation pharmacotherapy. Similar to genomic advancements in other fields, genomic information may be instrumental to recovery of tobacco use disorder and other substance use disorders (SUD). In fact, genomic data have been shown to predict smoking heaviness, smoking-related disease risk, likelihood of smoking cessation, and responsiveness to smoking cessation treatments. For instance, smokers with high-risk genomic variants in the *CHRNA5* nicotinic receptor gene were far less likely to successfully abstain from smoking than those with low-risk genotypes. Additionally, while smokers with high-risk genotypes responded to pharmacologic cessation treatments with a two-fold increase in abstinence, those with low-risk genotypes did not benefit from pharmacotherapy. Effective translation of these genomic findings may be critical to engaging high-risk patients and informing the most appropriate treatment approaches for smoking cessation. Within the SUD field, given that the science of genomic discovery is farthest along with respect to tobacco use disorder, the current research project focuses on the role of genomic medicine for smoking cessation.

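### The cognition-change mechanism question in 1.22 leaves genotype unadjusted, although genotype sets the RiskProfile message and predicts quitting

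*Combined protocol and SAP*

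**What the plan says.** - **Expectation (1.22).** More cessation and reduction is expected in the Intervention group, in particular among people who accept and remember their results and "whose health-related cognitions were altered (e.g., increased perceptions of disease risk, cessation benefits, value of cessation medications, self-efficacy". Every example of an alteration is a rise. No direction is set by genotype.
- **Regressions listed (1.22).** Genetic risk appears, with race and initial heaviness of smoking, as a predictor of whether results are accepted and remembered. Receipt of the RiskProfile is the predictor of quitting or cutting down. Genetic risk is not named as a covariate for the smoking outcome, and no listed model contains a cognition term.
- **Use of the result (1.4).** Mechanisms are to be examined under Aim 1, and Aim 2 adapts the RiskProfile "using evidence from Aim 1 on potential mechanisms that may identify elements that need to enhance potency of the intervention", alongside focus-group feedback.
- **The message (1.13).** The RiskProfile is built from the participant's own genetic data and covers "smoking-related genetic risk and likely responsiveness to medication", with graded risk labels. These data are obtained before randomisation, so they exist in both arms. Controls see their profile at the 6-month follow-up.
- **Genotype and outcome (1.5, C2).** Smokers with high-risk *CHRNA5* variants "were far less likely to successfully abstain from smoking than those with low-risk genotypes". Medication doubled abstinence in the high-risk genotypes, whereas "those with low-risk genotypes did not benefit from pharmacotherapy".

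**The concern.** On the plan's own account, genotype is a common cause of the two things that the mechanism question relates. It fixes the message, which should influence whether perceived risk or perceived value of medication rises, and it independently predicts quitting. Because cognition change happens after randomisation, randomisation does not balance genotype between people whose cognitions rose and people whose cognitions did not. An unadjusted comparison would then mix the effect of a changed belief with the effect of the genotype behind it.

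There is a second, narrower problem. The expectation joins accurate recall with a rise in the perceived value of medication. A participant who correctly remembers a low-response result would not be expected to value medication more, so the two conditions can conflict in that group.

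At stake is the Aim 1 mechanism evidence. A working mechanism could be hidden, or an inert one could look active, and that evidence is one of the two sources for adapting the RiskProfile. A larger sample would not remove this bias.

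**Working it through.** The plan states no effect size, power or alpha for this question, so there is no figure to reproduce. The check asks what an unadjusted comparison would show under two genotype strata, high-risk (H) and low-risk (L).

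**Inputs from the documents.** Direction of the genotype effect on quitting (H lower); medication ratio 2 in H and no benefit, read as 1, in L; overall quitting of about 5% (all 1.5); about 250 participants (1.12).

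**Assumed inputs.** Share of H, *s*: 0.3, 0.5, 0.7. Probability that the cognition rises, *a*H / *a*L: 0.6/0.4, 0.7/0.3, 0.8/0.2. Quit rates *q*H / *q*L: 5%/10% and 4%/12%, with 10%/5% as a reversed case.

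**Step 1: no true cognition effect.**

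Quit rate if raised = [*s*·*a*H·*q*H + (1−*s*)·*a*L·*q*L] / [*s*·*a*H + (1−*s*)·*a*L]. For not raised, replace each *a* by 1−*a*.

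Worked case, *s* = 0.5, 0.7/0.3, 5%/10%:
- raised: (0.0175 + 0.0150) / 0.50 = 6.5%
- not raised: (0.0075 + 0.0350) / 0.50 = 8.5%
- ratio 0.76, although belief does nothing.

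| *s* | *a*H/*a*L | *q*H/*q*L | raised | not raised | ratio |
|---|---|---|---|---|---|
| 0.3 | 0.6/0.4 | 5%/10% | 8.04% | 8.89% | 0.90 |
| 0.5 | 0.7/0.3 | 5%/10% | 6.50% | 8.50% | 0.76 |
| 0.7 | 0.8/0.2 | 4%/12% | 4.77% | 9.05% | 0.53 |
| 0.7 | 0.6/0.4 | 10%/5% | 8.89% | 8.04% | 1.11 |
| 0.5 | 0.8/0.2 | 10%/5% | 9.00% | 6.00% | 1.50 |

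These rows include the extremes of the grid: 0.53 to 0.90 when H quits less, 1.11 to 1.50 when H quits more. Within each genotype the ratio is 1.00 by construction, so stratifying or adjusting recovers it.

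**Step 2: weaker message gap.** With *s* = 0.5, 0.5/0.4 and 5%/10%: raised (0.0125 + 0.0200) / 0.45 = 7.22%; not raised (0.0125 + 0.0300) / 0.55 = 7.73%. The difference is −0.5 points, ratio 0.93.

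**Step 3: sign.** If everyone in H took medication and doubled from 5% to 10%, H would equal L at 10% and the Step 1 bias would vanish. A reversal needs a genotype gap below two-fold together with wide medication use. The documents give neither figure.

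**Step 4: medication beliefs.** Assume that a raised belief leads to medication use, so the ratio within H is 2 and within L is 1. Take *a*H/*a*L of 0.5/0.5, 0.7/0.3 or 0.8/0.2, with the same shares and quit rates of 5%/10% or 4%/12%. The pooled crude ratio runs from 0.84 to 1.54. For *s* = 0.5, 0.7/0.3, 4%/12%: raised (0.35×0.08 + 0.15×0.12) / 0.50 = 9.2%; not raised (0.15×0.04 + 0.35×0.12) / 0.50 = 9.6%; ratio 0.96. A real doubling in half the sample disappears.

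**Step 5: precision.** With 1:1 allocation (assumed) one arm is 125, or about 62 against 62. Power for 5% v 10% at two-sided 0.05 is 18%. In the worked case of Step 1, the 95% half-width is 1.96·√(0.065×0.935/62.5 + 0.085×0.915/62.5) = 9.2 points, against a bias of 2.0 points.

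**The case against.** **The plan does not define the comparison.** The sentence in 1.22 is an expectation, and a reader might infer a planned responder split that the documents do not describe. This stands. The fault is that a promised mechanism analysis is left unspecified, with genotype not named as a confounder.

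**The bias may be small and its sign is open.** Section 1.13 says that profiles differ only slightly, and Step 2 shows half a point under a weak message gap. Noise in a pilot of this size exceeds the bias. This also stands and limits the weight of the point. It does not remove the case for an adjustment that costs almost nothing.

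**Medication beliefs.** A reader might infer that a raised belief works in reverse in low-response genotypes. Section 1.5 supports no benefit, not harm, and the RiskProfile wording on medication response is in attachments that are not available. What remains is that a uniform rise is the wrong yardstick for that group.

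**Baseline cognition.** Section 1.13 says "we will ask baseline questions about smoking behaviors and genetic knowledge and then offer genetic testing to the participant", from which a reader might infer that beliefs are not measured at baseline. The V1 instrument is a listed attachment that cannot be seen, and 1.13 describes follow-ups that examine changes in attitude, so that inference is not supported.

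**Consequence.** Mechanism evidence is only one of two sources for the adaptation, and the study calls itself a pilot. Both are fair limits.

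**Conclusion.** The point holds as a gap in an exploratory analysis. From the plan's own statements, genotype drives the RiskProfile message and predicts quitting and medication response. An unadjusted comparison of participants by whether cognitions rose would be confounded by genotype, and 1.22 names no adjustment for it.

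The documents fix neither the size nor the sign. On the assumed grid, a null mechanism shows a crude ratio of 0.53 to 0.90 if high-risk genotypes quit less and 1.11 to 1.50 if they quit more; it comes closer to 1 if the message affects cognitions similarly across genotypes. Separately, a rise in the perceived value of medication does not suit participants with a low-response result. The randomised comparison of RiskProfile with brief counselling is not touched by any of this.

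**What to change.** In 1.22:

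1. Include genotype, as the RiskProfile risk and response category obtained before randomisation in both arms, as a covariate or stratum in the cessation and mechanism models.
2. Report arm differences in perceived risk and in perceived value of medication by that category, and state the expected direction of medication belief for each category.
3. Test the mechanism as a pathway in both arms (arm, then 30-day cognition, then 6-month smoking), adjusted for genotype, baseline smoking and, where V1 collects it, baseline cognition. Use this instead of comparing participants by whether cognitions rose.
4. Label the pathway analysis exploratory and state its main assumption: adjusting for genotype removes this confounder, but not others such as motivation to quit.

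The cost is analysis wording and a little more modelling, with no new genetic data. Estimates within genotype categories will be imprecise at about 250 participants and should be read as such.
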